4.4.3 Laboratory Values

Clinical laboratory values will be evaluated for each laboratory parameter by subject for Extension Phase.

Abnormal laboratory values will be identified as those outside (above or below) the normal range. Reference (normal) ranges for laboratory parameters will be included in the clinical study report for this study. Descriptive summary statistics (eg, mean, SD, median, minimum, maximum for continuous variables, and number and percentage for categorical variables) for the laboratory parameters and changes from baseline will be evaluated by modal dose and visit.

Laboratory test results will be assigned a low-normal-high (LNH) classification according to whether the value was below (L), within (N), or above (H) the laboratory parameter's reference range. Within-treatment comparisons will be based on 3 by 3 tables (shift tables) that, for a particular laboratory test, compare the Study Baseline LNH classification to the LNH classification at end of study/early termination, by modal dose.

Clinical laboratory results post-baseline will be evaluated for markedly abnormal values. A laboratory test will be considered markedly abnormal if the result worsens to meet Eisai grading criteria for laboratory values limit of Grade 2 or higher. If the Grade 2 limit is missing, the Grade 1 limit will be considered. [Appendix 12.1](#) presents the Eisai grading criteria for laboratory values that were used to identify subjects with markedly abnormal laboratory values. For the incidence of markedly abnormal laboratory values, each subject may be counted once in the laboratory parameter value high and in the laboratory parameter low categories as applicable.

While this section covers laboratory data starting from Extension Phase baseline, laboratory data before Extension Phase might be presented if deemed appropriate.

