2.2 Overall Study Design and Plan

2.2.1 Extension Phase

The Extension Phase comprises a 30-month Maintenance Period (Treatment Period) and a 14-day Follow-Up Period.

Subjects who complete the Core Study End of Study (EOS) Visit within 30 days prior to enrollment in the Extension Phase will be eligible for participation.

For subjects continuing directly from the Core Study to the Extension Phase, the End of Study (EOS) Visit of the Core Study will be the start of the Extension Phase.

Subjects who complete the Core Study, but who do not elect to immediately roll over to the Extension Phase will be required to return to the site within 30 days of completion of the Core Study and repeat selected assessments before being dispensed drug for the Extension Phase. If subjects return before 30 days of the last study visit, the tests that are required at that time are vital signs, weight, the Sleep Disorders Inventory (SDI), and the electronic Columbia-Suicide Severity Rating Scale (eC-SSRS). All other data will be carried over from Visit 6A. If subjects return on Day 30, all tests listed for Visit 6B will be performed. Details are as in (Figure 1).

During the Treatment Period, all subjects initially will receive lemborexant 10 mg per day (LEM10). At the discretion of the investigator, subjects will have the option of increasing the dose to lemborexant 15 mg per day (LEM15) or decreasing to lemborexant 5 mg per day (LEM5). All dose adjustments will be performed at an unscheduled visit or at the next scheduled visit.

All doses will be taken orally in tablet form each night for the duration of the Extension Phase immediately (ie, within 5 minutes) before the time the subject intends to sleep. The dose can be adjusted more than once during the Extension Phase. Subjects will receive 1 or 2 tablets as described below:

- LEM5: one lemborexant 5-mg tablet
- LEM10: one lemborexant 10-mg tablet
- LEM15: one lemborexant 5-mg tablet and one lemborexant 10-mg tablet

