2.2.2 Follow-Up Period

The Follow-Up Period will be 14 to 18 days in duration and begins when subjects leave the clinic at the end of the Maintenance Period. Subjects and caregivers will return to the clinic at least 14 days but no more than 18 days after the end of the Maintenance Period for the End of Study Visit, including the recording of AEs and concomitant medications, and assessment of clinical laboratory tests, vital signs, and weight, and measurement of an electrocardiogram (ECG).

Treatment in the Extension Phase will last for a maximum duration of 30 months or until the lemborexant clinical development program for Irregular Sleep-Wake Rhythm Disorder (ISWRD) is discontinued. A study design that includes the Extension Phase is presented in [Figure 1](#).

[figure not shown]

Figure 1 Study Design

Note: Visit -1 is an optional Prescreening Period for subjects and caregivers who are unsure whether the subject has Irregular Sleep-Wake Rhythm Disorder (ISWRD). Subjects will wear an activity tracker for approximately 4 days, then return to the site to have the data from the activity tracker downloaded and analyzed to determine whether they are candidates for the study. (revised per Amendment 05)

Note: Visit 2 is a caregiver visit for downloading actigraphy data to determine eligibility; Visit 3 is the baseline visit for both subject and caregiver; Visit 4 is a visit for both subject and caregiver to download actigraphy data and perform safety assessments; Visit 5 is the end-of-treatment assessments visit; and Visit 6A is for end-of-study assessments for the Core Study. For subjects continuing directly from the Core Study into the Extension Phase, Visit 6A will be the start of the Extension Phase. Subjects who complete the Core Study, but who do not elect to immediately continue into the Extension Phase have up to 30 days after Visit 6A to participate. These subjects will be required to repeat selected assessments (Visit 6B) before being dispensed drug for the Extension Phase. Some subjects will have fewer visits based on the availability of lemborexant commercially.

ISWRD = Irregular Sleep-Wake Rhythm Disorder, V = Visit.

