4.2.5 Prior and Concomitant Therapy

All investigator terms for medications recorded in the eCRF will be coded to an 11-digit code using the World Health Organization Drug Dictionary (WHO DD) (Mar 2016 or latest version). The number (percentage) of subjects who take prior and concomitant medications will be summarized on the Safety Analysis Set by modal dose group, Anatomical Therapeutic Chemical class (ATC), and WHO DD -preferred term (PT).

Prior medications are defined as medications that stopped before the first dose of Extension Phase study drug.

Concomitant medications are defined as medications that (1) started before the first Extension Phase dose of study drug and continued at the time of the first dose of study drug, or (2) started on or after the date of the first Extension Phase dose of study drug to the last dose day plus 14 days. All medications will be presented in subject data listings.

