4.4.2 Adverse Events

The AE verbatim descriptions (investigator terms from the eCRF) will be classified into standardized medical terminology using the Medical Dictionary for Regulatory Activities (MedDRA). AEs will be coded to the MedDRA (Version 18.0 or higher) lower level term closest to the verbatim term. The linked MedDRA PT and primary system organ class (SOC) are also captured in the database.

A TEAE for Extension Phase is defined as an AE that emerges during Extension Phase treatment, having been absent during the interval between the end of the Core and before Extension Phase Baseline) or

- Reemerged during treatment, having been present at pretreatment (Baseline) but stopped before treatment, or
- Worsened in severity during treatment relative to the pretreatment state, when the AE is continuous.

Only those AEs that are treatment-emergent will be included in summary tables. All AEs, treatment-emergent or otherwise, will be presented in subject data listings. AEs will be classified as TEAEs up to 14 days after the last study treatment.

An overview of the TEAEs will be summarized by modal dose group, including the number and percentage of subjects who experience TEAEs, treatment-related TEAEs, severe TEAEs, TEAEs leading to death and discontinuation from study/study drug.

The incidence of TEAEs will be reported as the number (percentage) of subjects with TEAEs by SOC and PT. A subject will be counted only once within an SOC and PT, even if the subject experienced more than 1 TEAE within a specific SOC and PT. The number (percentage) of subjects with TEAEs will also be summarized by maximum severity (mild, moderate, or severe). The number (percentage) of non-serious TEAEs with an incidence of greater than 5% will be summarized.

The number (percentage) of subjects with TEAEs will also be summarized by relationship to study drug (Yes [related] and No [not related]). Treatment-related TEAEs include those events considered by the investigator to be related to study treatment.

The number (percentage) of subjects with TEAEs leading to death will be summarized by MedDRA SOC and PT for each modal dose. A subject data listing of all AEs leading to death will be provided.

The number (percentage) of subjects with treatment-emergent SAEs will be summarized by MedDRA SOC and PT for each modal dose. A subject data listing of all SAEs will be provided.

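### The only laboratory shift table ends on a post-treatment value, and the visit windows give off-drug values numbered Extension visit labels

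*SAP*

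**What the plan says.** **Shift table.** Section 4.4.3 gives one shift display for laboratory data, in low/normal/high classes. It is to "compare the Study Baseline LNH classification to the LNH classification at end of study/early termination, by modal dose". By contrast, the ECG shift tables in 4.4.5 are by visit.

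**When the final visits occur.** Section 2.2.1 states: "The Extension Phase comprises a 30-month Maintenance Period (Treatment Period) and a 14-day Follow-Up Period". Section 2.2.2 then states: "Subjects and caregivers will return to the clinic at least 14 days but no more than 18 days after the end of the Maintenance Period". It lists laboratory tests, vital signs, weight and ECG among the assessments at that visit. For a subject who stops drug early, section 2.2.1 asks for an Early Termination Visit within 2 weeks of discontinuation.

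**Visit windows.** Section 7.1.4 assigns all efficacy and safety data to derived visits, and section 8 repeats this. The table lists Visit 6B and Extension Visits 7 to 15, then continues with the rule X-14 to X+15. It has no row for End of Study, Early Termination or follow-up, and no limit tied to the last dose.

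**Post-treatment limits elsewhere.** For adverse events, section 4.4.2 says: "AEs will be classified as TEAEs up to 14 days after the last study treatment". Section 4.2.5 uses the same 14 days for concomitant medications. No limit is stated for laboratory, vital-sign or ECG values.

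**The concern.** The objective of the Extension Phase is long-term safety and tolerability, and no hypothesis is tested. The descriptive safety tables are therefore the main product of the analysis.

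A shift table by modal dose will be read as showing what happened on that dose. As specified, it shows completers after about two weeks off drug, and early terminators at anything from the day of stopping to two weeks later. The two groups share one column under the same dose label. A change that appears on drug and resolves after stopping can leave no trace in it.

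The windows have a related fault. The time point on which 4.4.3 relies is not a derived visit in 7.1.4, although 7.1.4 claims all safety data. If the windows are applied as written, off-drug values enter numbered visits in the by-visit laboratory and vital-sign summaries and in the ECG displays. There they can sit beside other subjects' on-drug values.

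**Working it through.** **1. Time off drug in the shift-table column.** Assume that the last dose coincides with the end of the Maintenance Period, or with discontinuation.
- Completers (section 2.2.2): d = 14 to 18 days, never 0.
- Early terminators (section 2.2.1): d = 0 to 14 days.
- Combined column: 0 to 18 days. No completer contributes an on-treatment value.

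**2. What the markedly abnormal rule catches.** Section 4.4.3 counts Grade 2 or higher, or Grade 1 where no Grade 2 limit exists. The uncaught band is therefore Grade 1 where a Grade 2 limit exists. Examples from Appendix 12.1:
- ALT or AST above ULN to 3.0 x ULN
- bilirubin or creatinine above ULN to 1.5 x ULN
- hemoglobin below LLN to 10.0 g/dL

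A change in this band that has resolved by the final visit appears in neither display. Low sodium at Grade 1 would be counted, because its Grade 2 entry is N/A.

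**3. Reproducing the windows.** Target for Visit n: X = 73 + 30(n - 7); window: X-14 to X+15.
- Visit 8: X = 103, window 89-118, as printed.
- Visit 15: X = 73 + 240 = 313, window 299-328, as printed. The rows between also match.
- The next window starts at X + 30 - 14 = X + 16, one day after X + 15. The windows are contiguous, so every later study day belongs to some numbered visit.

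**4. Where off-drug values land.**

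*Stopping early (example).* Last dose on day 103. An Early Termination Visit 0 to 14 days later falls on days 103-117, all labelled Visit 8 (89-118). If treatment ends on day 103 and an End of Study Visit follows at 14 to 18 days (117-121), days 117-118 are Visit 8 and days 119-121 are Visit 9. Subjects still on drug can have values in the same windows. Section 2.2.2 expects treatment to end early for some: "Some subjects will have fewer visits based on the availability of lemborexant commercially".

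*Completing 30 months.* Assume the first Extension dose is on day 73 - 30 = 43 for direct rollover. Others enter later, since they "have up to 30 days after Visit 6A to participate"; write k = 0 to 30 for the delay in days. Visit 36 is 929-958 and Visit 37 is 959-988.

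| 30 months taken as | Last treatment day, k = 0 | End of Study, k = 0 | Label | Others whose last treatment day has that label |
|---|---|---|---|---|
| 913 days | 43 + 913 = 956 | 970-974 | Visit 37 | k = 3 to 30 (days 959-986) |
| 900 days | 43 + 900 = 943 | 957-961 | 957-958 Visit 36; 959-961 Visit 37 | k = 0 to 15 (943-958) Visit 36; k = 16 to 30 (959-973) Visit 37 |

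Off-drug and on-drug days share labels under either month length. Whether samples are taken on those on-drug days depends on the visit schedule, which is not in the SAP.

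**5. Which cut would separate them.**
- Last dose + 14 days: all 15 Early Termination days (0-14) and End of Study day 14 still count as on-treatment. The mixing remains.
- Last dose date: only an Early Termination sample on that date counts; no End of Study sample does.
- Last dose + 1 day: Early Termination days 0 and 1 count; no End of Study sample does.

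**The case against.** A comparison of baseline with the final visit is a recognised display, and 4.4.3 states it openly. On-treatment laboratory values are not discarded. They stay in the by-visit statistics, in the markedly abnormal counts (which use all post-baseline results) and in the listings; QTcF maxima per subject are also kept. No inference depends on the table. Derivation rules and table shells are held in separate documents, which may define a follow-up visit. A numbered label is not wrong in itself, since the Core Study numbers its own end-of-study visit 6A. In the 913-day rollover case above, a subject's own last treatment day (Visit 36) and End of Study (Visit 37) are separated.

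Much of this stands, and it limits the point to attribution and labelling. It does not remove it. Section 8 says that the windows described in the SAP will be used, and the only continuation rule stated is the same 30-day block. Separation within one subject does not prevent pooling across subjects.

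Two stronger readings are tempting and are not supported.
- A reader might note that End of Study on days 15 to 18 lies beyond the 14-day limit and call it a breach. That limit governs adverse events and concomitant medications only; the SAP sets none for laboratory values. A day-14 sample is as much post-treatment as a day-15 one.
- A reader might treat every day position as equally likely and quote the resulting share of visits that fall in a given window as the size of the problem. Such shares ignore the sampling schedule and do not measure harm.

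**Conclusion.** The point holds. As written, the one laboratory shift table mixes 0 to 18 days off drug and contains no on-treatment value for completers. The windows in 7.1.4 place End of Study and Early Termination values under numbered Extension visits.

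The practical loss is narrow. A Grade 1 change, where a Grade 2 limit exists, that reverses after stopping can be absent from both the shift table and the markedly abnormal counts. By-visit laboratory, vital-sign, weight and ECG summaries can also mix off-drug with on-drug values. A reader might infer that on-treatment safety data are lost; the SAP does not support that. The number of subjects affected cannot be derived from it.

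This rests on three assumptions:
- The last dose coincides with the end of the Maintenance Period or with discontinuation.
- The combined column is one classification; the SAP nowhere says that the two visits are shown separately.
- The Early Termination Visit includes the assessments concerned. The SAP defines it by reference to the Core Study end-of-study visit without itemising it, but 4.4.3 does classify laboratory values there.

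The conclusion concerns the SAP text, not the unseen programming documents. The change should be made before database lock.

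**What to change.** **Section 4.4.3.** Base the shift table on the last post-baseline value on or before the last dose date, and preferably add a second table on the worst such value. A cut of at most a day or so after the last dose is also workable: dosing is nightly, so a sample drawn the next morning carries the following date. Do not use last dose plus 14 days, for the reason in step 5 of the working. Show End of Study/Early Termination as a separate column labelled as post-treatment.

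**Section 7.1.4.** Restrict the numbered visits to values within the same cut, and add a derived visit, 'Follow-up (off drug)', for later values. Apply this to laboratory, vital-sign, weight and ECG data. The 14-day rules for adverse events and concomitant medications can stay as they are, since they serve a different purpose.

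**Cost.** SAP wording, one on-treatment flag and one or two extra tables, all from data already collected. Because the sampling schedule is not in the SAP, the last on-treatment sample may precede the last dose by some time. Reporting that interval beside the table would make this visible.

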Study visits, either in person or by telephone, will be conducted according to the Schedule of Procedures and Assessments for the Extension Phase. If the phone visit indicates an ongoing adverse event (AE), the subject should be brought to the clinic for an Unscheduled Visit. Subjects may discontinue from study drug for any reason. A subject who prematurely discontinues taking study drug should return to the clinic within 2 weeks of discontinuation to complete an Early Termination (ET) Visit. The assessments of the ET Visit are the same as those for the EOS Visit for the Core Study.

If the subject discontinues from the study due to an AE, the subject must complete an ET Visit, and the AE must be followed to resolution for a period of 4 weeks, whichever comes sooner.

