2.2.1 END OF EXTENSION PHASE

The End of the Extension Phase will be the date of the last study visit for the last subject in the Extension Phase.

Duration of Treatment: Up to 30 months or until the lemborexant clinical development program for ISWRD is discontinued.

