4 STATISTICAL METHODS

All descriptive statistics for continuous variables will be reported using mean, standard deviation (SD), median, minimum and maximum. Categorical variables will be summarized as number (percentage) of subjects.

There will be no hypothesis testings, and data will be only be summarized by timepoint and by modal dose received by the subject.

Modal dose will be calculated as follows:

If subject has one dose start date and no dose end date, then subject has been on initial10 mg dose, model dose = 10 mg.

If a subject has start dose date and only one end date, and a second dose start date; then subject has been on 10 mg dose till first end dose date, the number of days on 10 mg is calculated as follows: first end date - first start date +1 , and number of days on the new dose is calculated as: database snapshot date- second start date +1. The modal dose is the most frequent of these two numbers, ... and so on.

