5 INTERIM ANALYSES

Interim analyses will be performed for this study to provide data for a synoptic report to support new drug applications.

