7.1.2 Handling of Missing Data, Dropouts, and Outliers

Data will not be imputed, unless otherwise specified; i.e., all missing values will remain as missing in all statistical summaries and listings, unless otherwise specified.

Outliers: No formal statistical analyses will be performed to detect and/or remedy the presence of statistical outliers.

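### The laboratory shift table is scored only at end of study/early termination, so if it is produced at an interim no subject still on treatment can be scored

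*SAP*

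**What the plan says.** SAP Section 4.4.3 (Laboratory Values) bases its within-treatment laboratory comparisons on low/normal/high shift tables that "compare the Study Baseline LNH classification to the LNH classification at end of study/early termination, by modal dose". It gives these tables no visit, last-value or worst-value alternative.

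Other sections determine who has such a value at a given data cut:

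- **Section 5 (Interim Analyses):** "Interim analyses will be performed for this study to provide data for a synoptic report to support new drug applications". The number, dates and table list are not given.
- **Section 2.2.1 (End of Extension Phase):** the duration of treatment is "Up to 30 months or until the lemborexant clinical development program for ISWRD is discontinued".
- **Section 2.2.2 (Follow-Up Period):** subjects return "at least 14 days but no more than 18 days after the end of the Maintenance Period for the End of Study Visit", and laboratory tests are part of that visit.
- **Section 2.2.1 (Extension Phase):** the early termination visit is tied to stopping drug: "A subject who prematurely discontinues taking study drug should return to the clinic within 2 weeks of discontinuation to complete an Early Termination (ET) Visit".
- **Section 4 (Statistical Methods):** time on the current dose is counted as "database snapshot date- second start date +1", so subjects still on treatment are expected at a cut.
- **Section 7.1.2:** "all missing values will remain as missing in all statistical summaries and listings, unless otherwise specified".
- **Section 7.1.4:** the visit-window table has no end-of-study or early-termination row.

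In contrast, Section 4.4.5 presents ECG shift tables by visit, with an option to switch to post-baseline year.

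**The concern.** The rule suits a final analysis, when each subject has normally had one visit or the other. At an interim it selects subjects by whether they have left the study. Someone with many months of on-treatment laboratory results contributes nothing to the shift table, while someone who stopped after a few weeks does.

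Sections 4.4 and 7 place the table on the Safety Analysis Set, and nothing in Section 4.4.3 would tell a reader that ongoing subjects are absent. People who stop early may differ in tolerability from those who stay, so the shifts shown need not represent the treated group. Even if leavers and stayers are alike, the table would rest on few subjects, divided over modal-dose columns and nine cells per parameter. It would also describe a different population from the by-visit laboratory summaries beside it.

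**Working it through.** The SAP states no figure on this point (no dropout rate, entry period or interim date), so there is nothing to reproduce. The first two steps follow from the text; the last two rest on assumptions.

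**Step 1: who can be scored at a snapshot.**

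| Status at snapshot | End-of-study value | Early-termination value | In shift table |
|---|---|---|---|
| Still on treatment | no | no | no |
| Stopped early, visit done | no | yes | yes |
| Completed treatment and follow-up | yes | no | yes |
| Died or lost before either visit | no | no | no |

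Nothing is carried forward or imputed (Section 7.1.2), so the first row is empty whatever laboratory data exist.

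**Step 2: when the first completers appear.** Treatment lasts up to 30 months, and the End of Study Visit falls 14 to 18 days later. At about 30.4 days per month that adds 14/30.4 = 0.46 to 18/30.4 = 0.59 month, so about 30.5 months after the first Extension Phase dose. Before then, unless treatment ends early for programme reasons, every scored subject is an early termination.

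**Step 3: how many are scored.** Assumptions, none from the SAP:

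- uniform entry over A = 6, 12 or 18 months
- exponential dropout with a cumulative proportion d = 20%, 40% or 60% over 30 months, so λ = −ln(1 − d)/30
- End of Study Visit at 30.5 months
- every early leaver has a usable early-termination result.

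A subject with follow-up f months has left early with probability 1 − exp(−λ·min(f, 30)). If f is at least 30.5, the subject has completed with probability 1 − d.

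Worked case, A = 12, d = 40%, snapshot at month 24: λ = −ln(0.6)/30 = 0.01703, and follow-up is spread evenly over 12 to 24 months. Proportion scored = 1 − [exp(−0.2043) − exp(−0.4087)]/(0.01703 × 12) = 1 − (0.8152 − 0.6645)/0.2043 = 0.26.

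Ranges over the nine combinations of A and d before completers appear:

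| Snapshot (months after first dose) | Scored, % of entered | Early terminations, % of scored |
|---|---|---|
| 12 | 4–24 | 100 |
| 24 | 10–47 | 100 |
| 30 | 14–56 | 100 |

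Once completers appear, early terminations make up 37–90% of those scored at month 33, 21–82% at month 36 and 20–70% at month 42.

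**Step 4: possible distortion (illustration only).** Let p be the proportion who have left, and suppose the normal-to-abnormal shift rate is 30% in leavers and 10% in ongoing subjects. Before any completers the table shows 30%. The all-subject rate is p × 0.30 + (1 − p) × 0.10:

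- p = 0.10: 0.03 + 0.09 = 12%
- p = 0.25: 0.075 + 0.075 = 15%
- p = 0.40: 0.12 + 0.06 = 18%

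If both groups shift at 10%, the table and the all-subject rate agree and only the small number scored remains a problem.

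**The case against.** The case for leaving the plan alone has several sound parts.

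- **The interim table list is unknown.** Section 5 says only that interim analyses supply data for a synoptic report, and table shells are in a separate document (Section 10). A reader might infer that this table will support a new drug application. The SAP does not say so, and the point is therefore conditional on the table being produced at an interim.
- **Ongoing subjects are covered elsewhere.** Section 4.4.3 also gives by-visit summaries and counts of markedly abnormal post-baseline values, and Section 7.1.3 lists individual data. A reader might infer that laboratory signals in ongoing subjects are hidden; they are not.
- **Dropouts need not dominate.** Treatment may end when the ISWRD programme is discontinued, and the note to Figure 1 says commercial availability will mean fewer visits for some subjects. Such exits are not selected for poor tolerability. After the first completers the mix can favour them.
- **Differential bias by modal dose is not shown.** It is tempting to argue that early leavers fall into the 10 mg column because they stop before any dose change. Under Section 4 a subject without a dose change is in that column whether stopped or ongoing, so this does not establish that bias differs between columns.
- **Programming rules are in separate documents** (Section 8), so an interim timepoint may be defined there. That is possible, but the SAP names one timepoint, and a specification that follows it faithfully would leave ongoing subjects out.

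These points limit the consequences. None gives an ongoing subject a post-baseline classification under the rule as written.

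**Conclusion.** The point holds in conditional form and is worth correcting. That a subject on treatment at an interim snapshot cannot be scored follows from the text alone. That the table then holds only early terminations is certain until the first subjects complete treatment and follow-up, unless the programme is discontinued or treatment otherwise ends early. Later the composition depends on an interim date the SAP does not give, so a general statement that the table describes mainly dropouts is not supported.

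The percentages scored rest on assumed entry and dropout, and any figure for bias is an assumption. The consequence is confined to one descriptive table in a study without hypothesis tests. The final analysis is largely unaffected; the exception is subjects who die or are lost before an early termination visit, whose number cannot be judged from the SAP.

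**What to change.** In Section 4.4.3, define the post-baseline side of the shift table for every Safety Analysis Set subject with a post-baseline result as the last available on-treatment value up to the snapshot or last dose, whichever is earlier. Add a version using the worst on-treatment value, with low and high taken separately. Alternatively, present laboratory shifts by visit or post-baseline year, as Section 4.4.5 does for ECG. The end of study/early termination table can stay alongside. State the number of subjects scored in each table, by modal dose.

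The cost is SAP wording and one or two more versions of an existing table, from data already collected. A small downside is that the last value falls at different treatment durations across subjects, so a summary of time on treatment at that value would help the reader.
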